7.1 Adverse Events Reporting

While this is a low risk exercise intervention study that does not involve the use of a drug or medical device, the PI will be responsible for the identification and documentation of adverse events and serious adverse events, as defined below. At each study visit or assessment, the PI or designee must assess, through non-suggestive inquiries of the subject or evaluation of study assessments, whether an Adverse Event or Severe Adverse Event has occurred.

An adverse event (AE) is any untoward medical occurrence in a subject receiving study intervention and which does not necessarily have a causal relationship with this treatment. For this protocol, the definition of AE also includes worsening of any pre-existing medical condition. An AE can therefore be any unfavorable and unintended or worsening sign (including an abnormal laboratory finding), symptom, or disease temporally associated with the use of study intervention, whether or not related to use of the study intervention. Abnormal laboratory findings without clinical significance (based on the PI's judgment) should not be recorded as AEs. But laboratory value changes that require therapy or adjustment in prior therapy are considered adverse events.

Serious adverse events (SAEs) are adverse events that result in any of the following outcomes: death, life-threatening adverse event in the view of the investigator its occurrence places the patient at immediate risk of death, inpatient hospitalization or prolongation of existing hospitalization, a persistent or significant incapacity

or substantial disruption of the ability to conduct normal life functions, or a congenital anomaly/birth defect. All SAEs will be reported to the DUHS IRB within 24 hours for life-threatening events and within 5 business days for non-life-threatening events

From the time the subject signs the informed consent form through the End of Study visit, all AEs/SAEs must be recorded in the subject adverse events case report form. AEs will be assessed according to the CTCAE version 4.0. If CTCAE grading does not exist for an AE, the severity of the AE will be graded as mild (1), moderate (2), severe (3), life-threatening (4), or fatal (5).

In addition to severity, all AEs will be graded as:

- Definite: The AE is clearly related to the study intervention
- Probably: The AE is likely related to the study intervention
- Possible: The AE may be related to the study intervention
- Unlikely: The AE is doubtfully related to the study intervention
- Unrelated: The AE is clearly NOT related to the study intervention

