3.2 Patient Exclusion criteria

- 1) Both patient and caregiver are unable to read and follow directions in English (ok if only patient cannot read and follow directions in English as caregiver will be able to help).
- 2) Any absolute contraindications to exercise:
 - a) recent (< 6 months) acute cardiac event;
 - b) unstable angina;
 - c) uncontrolled dysrhythmias causing symptoms or hemodynamic compromise;
 - d) symptomatic aortic stenosis;

A Research Program Targeting Pre-, Peri-, and Post-transplant Optimization Program (R-POP)

Version 1.18: October 25, 2022

- e) uncontrolled symptomatic heart failure;
- f) acute pulmonary embolus;
- g) acute myocarditis or pericarditis;
- h) suspected or known dissecting aneurism; or
- i) coronary artery disease.

3) Functional impairment resulting in inability to exercise

In addition, patients who meet these inclusion and exclusion criteria and consent to participate will undergo cardiopulmonary exercise testing (CPET), with heart rate and rhythm will be monitored continuously using a 12-lead ECG. The ECG will be used to make sure the subject does not have any abnormalities before, during, and after the treadmill stress test. Results will be reviewed by a physician before the subject is cleared to participate in interval training. Therefore, a subject may meet inclusion and exclusion criteria, consent to participate, but then not meet cardiology clearance and therefore will be unable to participate in the intervention; these patients and their caregivers will then be transitioned off study.

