3.5 Subject Recruitment, Selection, and Consent

Potential patient subjects will be recruited from the Duke Adult Bone Marrow Transplant (ABMT) Program. Under the current standard of care practice, ABMT physicians evaluate all new patients. If the patient's ABMT physician deems the patient to be an allogeneic transplant candidate and suitable for Research POP (R-POP), and the patient expresses interest in participating, they will be referred to research staff, who will review inclusion/exclusion criteria and tell the patient more about the study. Both the ABMT physician, who will be a sub-investigator, and the research staff will make clear that participation in this trial is voluntary, and patients may decline to hear more or to participate without penalty; these patients will receive standard of care.

Those interested in learning more will meet with study staff who will explain details, answer questions, and confirm inclusion/exclusion criteria. Only subjects who voluntarily provide full informed consent will be included in the study.

Subjects who are screened but do not want to participate (do not give informed consent) will not be recorded and will receive standard care. They will be asked to complete a decline survey (Appendix D) in order to inform the investigators of why participation was declined and improve study design for future interventions.

Caregiver subjects will be identified by their patient as the patient's primary caregiver. They will be approached by study staff who will explain details, answer questions, and confirm inclusion/exclusion criteria. Only those who voluntarily provide full informed consent will proceed to study enrollment. Patients may decide to enroll without their caregivers deciding to enroll; in these cases, patients will participate in the study and caregivers will not participate in any research-related events. Caregivers may not enroll if their patient does not enroll.

This is a single arm feasibility study; all subjects will be assigned to the intervention group. We anticipate 35 patients will be consented and 30 patients to pass CPET/cardiology clearance to receive interval training. Up to 35 caregivers may consent and 30 caregivers participate, though this number may be lower depending on caregiver availability and consent.

A Research Program Targeting Pre-, Peri-, and Post-transplant Optimization Program (R-POP)

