4.8 Safety endpoints

Treatment-related mortality (TRM) and grade 3-4 adverse events as defined by the National Cancer Institute Common Terminology Criteria for Adverse Events (NCI-CTCAE) ¹³⁵ will be monitored that are related to study interventions (e.g. exercising).

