As noted in the exercise intervention section, in order to participate in the exercise intervention, subjects must first meet all inclusion and exclusion criteria and consent to participate, after which they will undergo cardiopulmonary exercise testing (CPET). CPET will be reviewed by a physician and subjects will not be able to participate in the intervention unless cleared by a physician. Therefore, not every patient who consents will participate in the intervention. Because our goal is to test the intervention in 30 patients, and assuming a 10% drop out rate (subjects who consent to participate but do not pass CPET testing), we will consent 35 subjects with the intent that 30 will participate in the intervention.

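### Section 7.1 ties the adverse event definition to receipt of the intervention but records events from consent, so harm from the study's own CPET can be graded unrelated or not counted

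*Combined protocol and SAP*

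**What the plan says.** All references are to the combined protocol and SAP.

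- **Definition (Section 7.1).** "An adverse event (AE) is any untoward medical occurrence in a subject receiving study intervention". The section goes on to cover any sign, symptom or "disease temporally associated with the use of study intervention, whether or not related to use of the study intervention".
- **Recording window (Section 7.1).** "From the time the subject signs the informed consent form through the End of Study visit, all AEs/SAEs must be recorded". The PI or a delegate must also check for events at every study visit or assessment.
- **Causality (Section 7.1).** There are five grades, from definite to unrelated. Each is worded against the study intervention, and none covers a study procedure.
- **Safety endpoint (Section 4.8).** Treatment-related mortality and grade 3-4 adverse events "will be monitored that are related to study interventions (e.g. exercising"). The opening of Section 7.0 has the same restriction, for grades 1-4.
- **Place of CPET.** The Section 4.0 table lists CPET as an assessment and interval training as the intervention. Section 4.1.1 puts CPET before the exercise intervention starts, and Section 6.2 makes physician clearance a condition of taking part in it.
- **Patients not cleared (Section 3.2).** "these patients and their caregivers will then be transitioned off study".
- **Numbers.** Section 3.5: "We anticipate 35 patients will be consented and 30 patients to pass CPET/cardiology clearance to receive interval training". Section 6.2: "assuming a 10% drop out rate (subjects who consent to participate but do not pass CPET testing"), and "we will consent 35 subjects with the intent that 30 will participate in the intervention".

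**The concern.** CPET is a maximal treadmill test done for the study. Section 7.0 names chest pain and exacerbation of coronary disease among its risks. If the rules that decide what counts as an adverse event refer only to the intervention, and the test is not part of the intervention, harm caused by the test has no clear place in the safety results.

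Three things are at stake. Two careful raters could classify the same CPET event differently. SAE reporting depends on the AE definition, because Sections 7.1 and 7.2 both define an SAE as a kind of AE; an event read as not an AE would not start the IRB reporting clock (24 hours or 5 business days). And Section 6.2 describes a safety and feasibility study, which Section 7.0 says would inform a randomized phase 2 trial. The clearance test is part of the programme as delivered, so its harms belong in the safety account.

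**Working it through.** **Step 1. Apply each rule literally to a CPET event.**

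| Rule | Baseline CPET, patient not cleared | Repeat CPET, cleared patient |
|---|---|---|
| 7.1 definition | Not met if the intervention means interval training: the patient never receives it | Met: the patient is receiving the intervention |
| 7.1 recording window | Inside: CPET follows consent | Inside |
| 7.1 causality | Only the intervention can be the cause; unrelated is a permitted grade | Same |
| 4.8 endpoint | Left out if graded unrelated | Left out if graded unrelated |
| 7.1/7.2 SAE | Depends on being an AE first | Can be an SAE |

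A baseline CPET event in a patient who is later cleared sits between the columns: at the time of the test that patient has not yet received training either.

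The left column contains the contradiction. The window puts the event on the AE form; the definition can be read to say there is no AE to record. In both columns the causality scale lets a rater follow the rules and grade a CPET-caused event unrelated, which removes it from the endpoint.

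**Step 2. How many patients are on the not-cleared path.**

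The plan's own figure: 30 to be treated with 10% lost at CPET gives 30 / (1 − 0.10) = 33.3, rounded up to 34; the simpler 30 × 1.10 gives 33. The stated 35 is within two patients of either.

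- By planned counts: (35 − 30) / 35 = 5/35 = 14.3%.
- By the stated assumption: 35 × 0.10 = 3.5 patients.

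So the range is 10% to 14.3%, or about 3.5 to 5 of 35 patients.

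**Step 3. How many tests are affected.**

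The Section 4.0 table lists five CPET time points: new patient evaluation, sign-off, day 30, discharge and day 180. With 35 baseline tests and four repeats in 30 patients, 35 + 4 × 30 = 155. Day 30 is done only if the patient is medically stable; without it, 35 + 3 × 30 = 125. The 155 is a ceiling, since deaths and withdrawals reduce it.

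**Step 4. What the unstated denominator changes.**

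With zero events, the one-sided 95% upper bound on an event rate is 1 − 0.05^(1/n).

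- n = 30: 9.5%.
- n = 35: 8.2%.

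The difference in precision is small. What matters is which patients' events are eligible to be counted.

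**The case against.** The strongest reply is that CPET events are already captured. Recording runs from consent, events are checked at each assessment, CPET is an assessment done after consent, and Section 7.4.1 has the PI tabulate adverse events continuously. A window that opens before training has little purpose if pre-training events are not AEs. Section 7.1 also says an AE need not be causally related, so the relatedness grade affects the endpoint and not whether the event is recorded.

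Nor is the term study intervention formally defined. The wording in Sections 4.8 and 7.0 is plural and gives exercising as an example; Section 7.0 calls CPET itself a form of exercise with risks. The Section 4.0 table also counts daily food tracking as an intervention, so a patient not cleared for training may not be wholly untreated. Clinical care after a CPET finding is covered: Section 7.0 provides an immediate medical response, notification of the primary provider, and referral.

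Most of this stands, and it limits the point. A reader might infer that CPET events are excluded outright; the recording rule and the open meaning of intervention do not support that. A reader might also infer that the safety table will rest on the 30 trained patients and so make the programme look safer. No section sets that denominator, and Section 6.2 frames its precision on 35. Nor do the documents show that patients who fail clearance are those most likely to be harmed by the test; failing clearance is not itself harm.

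The reply does not supply a causality category for study procedures, a statement in Section 4.8 on whether CPET-related events count, or a safety population.

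**Conclusion.** The point holds as an internal conflict in Section 7.1 together with a gap in the causality scale and the Section 4.8 endpoint. A CPET-caused event, at baseline or at a repeat test, can be graded unrelated and left out of the endpoint by someone following the text. At the baseline test in a patient who then leaves the study, it can also be read as not an AE or SAE.

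The not-cleared path involves 10% (stated assumption) to 14.3% (planned counts) of 35 patients; the relatedness gap applies to every CPET, at most 155. The documents give no CPET event rate, so the effect on the reported safety rate cannot be estimated.

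This rests on reading CPET as an assessment distinct from the intervention. Sections 4.0, 4.1.1 and 6.2 favour that reading, and Section 7.0 partly cuts against it. If the authors meant CPET to be included, the change below only makes their intention explicit.

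**What to change.** 1. In Section 7.1, drop the limit to patients receiving the intervention and define an AE as any untoward medical event from signature of consent onward. This brings the definition into line with the recording window and settles SAE status.
2. Word all five causality grades as relatedness to *the study intervention or a study procedure, including CPET*.
3. Make the same change in Section 4.8 and in the opening of Section 7.0.
4. State the safety population as all patients who start at least one CPET (up to 35).
5. Tabulate CPET-related and training-related events separately, including CPET events in patients who are not cleared.

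The cost is wording in three places and one extra table. It adds no tests and leaves the clearance rule and CPET schedule as they are; checks at each assessment are already required. The reported event rate may be higher.

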7.2 Serious Adverse Events (SAE)

An AE is considered “serious” if in the opinion of the investigator it is one of the following outcomes:

- Fatal
- Life-threatening
- Constitutes a congenital anomaly or birth defect
- A medically significant condition (defined as an event that compromises subject safety or may require medical or surgical intervention to prevent one of the three outcomes above).
- Requires inpatient hospitalization or prolongation of existing hospitalization
- Results in persistent or significant incapacity or substantial disruption to conduct normal life functions.
-

7.3 Reporting of SAEs

SAEs will be reported to the DUHS IRB within 24 hours, for life-threatening events, and within 5 business days for non-life-threatening events

7.4 Quality Control and Quality Assurance

This is a low risk intervention study that does not involve an agent or device. The study still involves some level of risk due to the subject population and therefore might be subject to safety and monitoring by the DCI SOC and the DCI monitoring team.

7.4.1 Monitoring

This clinical research study will be monitored both internally by the PI and institutionally by the Duke Cancer Institute (DCI). In terms of internal review, the PI will continuously monitor and tabulate adverse events. Appropriate reporting to the Duke University Medical Center IRB will be made. If an unexpected frequency of Grade III or IV events occur, depending on their nature, action appropriate to the nature and frequency of these adverse events will be taken. This may require a protocol amendment, dose de-escalation, or potentially closure of the study. The PI of this study will also continuously monitor the conduct, data, and safety of this study to ensure that:

- Risk/benefit ratio is not altered to the detriment of the subjects;
- Appropriate internal monitoring of AEs and outcomes is done;
- Over-accrual does not occur;
- Under-accrual is addressed with appropriate amendments or actions;
- Data are being appropriately collected in a reasonably timely manner.

A Research Program Targeting Pre-, Peri-, and Post-transplant Optimization Program (R-POP)

DCI review and monitoring of this protocol occurs in accordance with the NCI-approved Data and Safety Monitoring Plan. Briefly, protocol review begins with an initial review by the Cancer Protocol Committee (CPC), which assesses the ethics and safety of the protocol. Documentation of these assessments will be maintained. Formal, independent monitoring will be conducted by the DCI Monitoring Team after the first 3 subjects are enrolled, followed by annual monitoring of 1-3 subjects until the study is closed to enrollment and subjects are no longer receiving study interventions that are more than minimal risk. DCI Monitoring Team reports and additional data/safety/toxicity reports submitted by the PI will be reviewed by the Safety Oversight Committee (SOC) on an annual basis. Additional monitoring may be prompted by findings from monitoring visits, unexpected frequency of serious and/or unexpected toxicities, or other concerns. Monitoring visits may also be initiated upon request by DUHS and DCI Leadership, CPC, SOC, a sponsor, an investigator, or the IRB.

7.4.2 The Duke Cancer Institute Safety Oversight Committee (SOC)

SOC is responsible for annual data and safety monitoring of DUHS sponsor-investigator phase I and II, therapeutic interventional studies that do not have an independent Data Safety Monitoring Board (DSMB). The primary focus of the SOC is review of safety data, toxicities and new information that may affect subject safety or efficacy. Annual safety reviews includes but may not be limited to review of safety data, enrollment status, stopping rules if applicable, accrual, toxicities, reference literature, and interim analyses as provided by the sponsor-investigator. The SOC in concert with the DCI Monitoring Team oversees the conduct of DUHS cancer-related, sponsor-investigator therapeutic intervention and prevention intervention studies that do not have an external monitoring plan, ensuring subject safety and that the protocol is conducted, recorded and reported in accordance with the protocol, standing operating procedures (SOPs), Good Clinical Practice (GCP), and applicable regulatory requirements.

7.5 Audits

The Duke School of Medicine Clinical Trials Quality Assurance (CTQA) office may conduct confidential audits to evaluate compliance with the protocol and the principles of GCP. The PI agrees to allow the CTQA auditor(s) direct access to all relevant documents and to allocate his/her time and the time of the study team to the CTQA auditor(s) in order to discuss findings and any relevant issues.

CTQA audits are designed to protect the rights and well-being of human research subjects. CTQA audits may be routine or directed (for cause). Routine audits are selected based upon risk metrics generally geared towards high subject enrollment, studies with limited oversight or monitoring, Investigator initiated Investigational Drugs or Devices, federally-funded studies, high degree of risk (based upon adverse events, type of study, or vulnerable populations), Phase I studies, or studies that involve Medicare populations. Directed audits occur at the directive of the IRB or an authorized Institutional Official.

CTQA audits examine research studies/clinical trials methodology, processes and systems to assess whether the research is conducted according to the protocol approved by the DUHS IRB. The primary purpose of the audit/review is to verify that the standards for safety of human subjects in clinical trials and the quality of data produced by the clinical trial research are met. The audit/review will serve as a quality assurance measure, internal to the institution. Additional goals of such audits are to detect both random and systemic errors occurring during the conduct of clinical research and to emphasize “best practices” in the research/clinical trials environment.

The Duke University Office of Audit, Risk, and Compliance – Human Subjects Research Compliance (OARC HSRC) office may conduct confidential audits to evaluate compliance with the protocol and the principles of GCP. The PI agrees to allow the OARC HSRC auditor(s) direct access to all relevant documents and to allocate his/her time and the time of the study team to the OARC HSRC auditor(s) in order to discuss findings and any relevant issues.

8.0 DATA STORAGE AND CONFIDENTIALITY

The Principal Investigator will ensure that subject privacy and confidentiality of the subject's data will be maintained. Research Data Security Plans (RDSPs) will be approved by the appropriate institutional Site Based Research group.

To protect privacy, every reasonable effort will be made to prevent undue access to subjects during the course of the study. Prospective participants will be consented in an exam room where it is just the research staff, the patient and his/her family, if desired. For all future visits, interactions with research staff (study doctor and study coordinators) regarding research activities will take place in a private exam room. All research related interactions with the participant will be conducted by qualified research staff who are directly involved in the conduct of the research study.

To protect confidentiality, subject files in paper format will be stored in secure cabinets under lock and key accessible only by the research staff. Only a unique study number and subject initials will identify subjects. Electronic records of subject data will be maintained using a dedicated Microsoft Access database, which is housed in an encrypted and password-protected DCI file server and completed CRFs and demographic information will be stored and updated in REDcap and Duke Box. Access to electronic databases will be limited to study staff and clinical staff supporting the subject's care. The DCI and/or Duke Medicine will manage the security and viability of the IT infrastructure.

Upon completion of the study, research records will be archived and handled per DUHS HRPP policy.

Subject names or identifiers will not be used in reports, presentations at scientific meetings, or publications in scientific journals.

